4.4 Qualitative/Process Evaluation

Qualitative research will be conducted within the pilot phase of the study to understand the acceptability of the intervention and trial processes and inform the main study. Interviews will continue into the main study to understand patient recovery.

Objectives of the qualitative work are to understand:

1) The acceptability of the interventions and trial processes from the perspective of patients (cross-sectional study).

2) Patient's lived experience and acceptability of AKA and TKA surgery and the impact on quality of life and recovery (longitudinal study).

3) The implementation of TKA into clinical practice.

4.4.1 Intervention, trial acceptability and lived experience

All individuals who have consented to participate in the trial will be invited to participate to capture their experiences of the trial, acceptability of the trial processes, and views of TKA and AKA. Those who decline participation will also be invited to participate in relation to intervention acceptability and trial processes only. A purposive sample of maximum 48 patients to include both sexes, a range of ages, clinical presentation, socio-economic status (based on postcode converted to Index of multiple deprivation score), geography (region/site) (24), ethnicities and patients living with multi-morbidity. Guided by information power (22), with a narrow study aim and exploratory analysis, this sample size should provide sufficient data to address the associated research questions. Recruitment will end when the trial closes to recruitment, or when the final sample size is reached.

Patients will be approached to take part in an interview by the local research team. This will be following the participant's surgery and once clinically appropriate. For those who agree to receive further information, a 'consent to contact' form will be completed. The HAMLET qualitative researcher will then contact the patient by phone, email or post to discuss further.

Any patient who verbally gives consent to contact and subsequently agrees to take part in an interview, will be asked to provide written consent. If it is not possible for the patient to sign the consent form prior to the date of the interview, verbal consent will be taken at the start of the interview, and the associated audio recording saved. If a signed consent form is subsequently received the audio recording will be deleted. Patients may consent immediately, decline immediately, or defer their consent. Patients will have the option to have their partner or informal carer join them for the interviews, but this will not be a requirement of participation.

Initial interviews will take place eight to ten weeks post-operatively. Those who drop out of the study post randomisation may be interviewed at the point they drop out of the trial. Participants will also be invited to participate in a longitudinal interview study to gain insight into the impact on QoL and longer-term recovery (at 6, 12, 24 and where possible 36 months post amputation).

Interviews will take place face-to-face, telephone or video, depending on patient preference. The interview will be informed by a topic guide developed for the study with PPI input.

All interviews will be audio recorded using an encrypted dictaphone or directly onto a university laptop/PC (online interviews). Interviews will be transcribed, and

pseudoanonymised for analysis. Field notes will be taken after each interview and used in analysis.

Though the interview will focus on sensitive information and participants may describe distressful times and feelings, the interview itself should not cause distress. If any participants do become distressed or fatigued the interview will be paused or stopped. If appropriate, the patient's clinician will be contacted (e.g. GP).

4.4.2 Understanding trial conduct and intervention implementation issues

Regular meetings will be held with sites to explore how sites envisage implementing the study results into clinical practice. These meetings will enable identification and understanding of logistical barriers, set up delays and any difficulties with data collection or loss to follow-up, and to identify facilitators to optimise delivery of the trial protocol locally (25).

4.5 Studies Within a Trial (SWAT)

The HAMLET study will act as a host trial for two individual Studies Within a Trial (SWAT), designed to evaluate the effectiveness of either a participant recruitment or retention strategy. The protocols for each are available on the MRC SWAT repository (recruitment: SWAT 15 (26), retention: SWAT 180 (27)). As is usual with embedded trials, the sample size will be informed by the number of participants approached to participate in the main study (for the recruitment SWAT) or those participating in the study (for the retention SWAT).

4.5.1 Recruitment SWAT: The effectiveness of a study explanatory animation We will evaluate the effects of mode of presentation of the study design to participants on recruitment rate. Participants will be randomised (on a site basis) to receive an animated explanatory video (explaining the study) plus the standard patient information sheet (PIS) or just the PIS.

Successful clinical trial recruitment is an ongoing challenge, with a recent review estimating that 37% of trials fail to meet their recruitment targets (28). The PRioRiTy study of recruitment research prioritised "what are the best approaches

for designing and delivering information?" to potential participants as the fourth most important unanswered issue (29).

A review of recruitment strategies identified 35 studies focusing on information delivery, but almost all were low or very low methodological quality (30). Only three studies evaluated use of video information provision, with very low-GRADE certainty evidence. At the time of the review, no studies evaluated animations as a method of providing study information. The popularity of animations is however increasing and hence evaluation is required.

As is usual with embedded trials, the sample size is constrained by the number of patients approached about the study hence a formal power calculation to determine sample size has not been conducted.

This will be a cluster trial; randomisation will be carried out at the site level to reduce cross contamination. The allocation ratio will be 1 to 1. Generation of the allocation sequence will be undertaken independently by a researcher not involved with the recruitment of participants.

The primary outcome of this embedded trial will be the recruitment rate, i.e. the proportion of participants in each group who are randomised into the host trial. Secondary outcomes will include the proportion of patients in each group who are screened but do not go on to be randomised, and the cost effectiveness of the intervention.

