4.0 Trial Design

4.1 Design

The trial objectives will be addressed using a multicentre, two-arm, non-blinded, pragmatic, parallel group randomised controlled superiority trial.

The study will consist of a three-year recruitment phase, including the 12-month internal pilot phase, followed by the main recruitment period. Following collection of baseline measures, randomisation and treatment, all participants will be followed up for 24 months. Follow-up data will be collected from participants via a remote questionnaire every four months, at 4, 8, 12, 16, 20 and 24-months post randomisation.

The 12-month internal pilot will assess recruitment and retention and patient acceptability of both the intervention and trial processes. The pilot study will be set up in sites with existing surgical, rehabilitation and prosthetic experience of TKA, allowing additional time for other sites to receive training and support to implement or expand TKA services if required.

Semi-structured interviews will be conducted to include study participants, those who withdraw from the study and patients who decline to participate. The findings of these interviews will be used to inform aspects of trial design and delivery during this phase. These interviews will take place 8-10 weeks post-treatment.

To understand the longer-term impact of TKA and AKA on patient's lives and recovery, as part of the qualitative study, we will follow up a subgroup of 20-24 patients for up to 3 years, with interviews at 12, 24 and 36 months post-operatively.

A report will be provided to the funder at the end of the pilot phase and subject to their approval (assuming feasibility has been established) will proceed to the main trial.

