4.5.2 Retention SWAT: A cash vs voucher monetary incentive

Poor participant retention rates can have adverse consequences on the validity of randomised trials. There is a lack of evidence on efficient ways to retain participants in trials.

Monetary incentives consisting of either shopping/gift vouchers or cash are a common strategy used by trial teams to encourage participants to complete follow-up

questionnaires, attend follow-up assessment appointments or both. A previous review of strategies to improve retention in trials found monetary incentives may improve retention rates compared with no incentive; but the certainty of the evidence was low [1]. As a result, evaluation of monetary incentives as a retention method requires further evaluation.

We will evaluate the effect of an unconditional £25 shopping voucher incentive compared with an unconditional £25 cash incentive, provided before the 12 and 24 month follow up questionnaire. Participants will be asked to confirm their voucher preference at Baseline so that this can be provided should the participant be randomised to receive the voucher intervention.

As is usual with embedded trials, the sample size is constrained by the number of patients approached about the study hence a formal power calculation to determine sample size has not been conducted.

All participants recruited into the HAMLET trial, who remain as fully participating (i.e. have not fully withdrawn, withdrawn from postal follow up or have died) and who have yet to reach the 12-month time point will be eligible for the SWAT. There are no additional inclusion or exclusion criteria.

Generation of the allocation sequence will be undertaken independently by a researcher not involved with the follow up of participants. Participants will be allocated 1:1 using block randomisation, stratified by the host trial's treatment arm, using randomly varying block sizes to avoid imbalance between the SWAT intervention arms.

The primary outcome of this embedded trial will be retention rate, i.e. the proportion of participants who return their questionnaire in each group.

Secondary outcomes will be:

- 1) Cost-effectiveness (cost per participant retained)
- 3) Number of contact attempts with participants before completion of follow-up

assessment

4) Questionnaire completeness (e.g., primary outcome measure obtained)

The effects of the strategies in different patient populations will be explored, including sex, age and ethnic subgroups.

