10.6.1 Recruitment SWAT

An 'intention-to-treat' analysis will be performed including all randomised sites analysed in the SWAT group to which they were allocated.

Both demographic characteristics, including age, sex, and ethnic group of randomised participants and site characteristics, including geographical location and catchment size, will be presented descriptively as mean (standard deviation) or number (%), as appropriate.

The primary analysis will compare the difference in recruitment rates between those receiving the animation in addition to the PIL and those not receiving the animation. This outcome will be analysed using mixed effect logistic regression with a fixed effect for SWAT allocation and a random intercept for site.

Secondary analysis: The difference in the proportion of those responding to a recruitment invitation who received the animation in addition to the PIL but who do not go on to be randomised, and those not receiving the animation but who do not go on to be randomised will also be analysed using a similar model to the primary outcome.

The difference in cost per recruited participant between those offered the animation and those not offered the animation will be calculated. In addition to the direct costs of the animation, it may also be necessary to include the cost of staff time spent administering the recruitment packs.

The following sensitivity analyses will be performed for the primary analysis:

• Excluding participants who did/could not receive allocation as randomised.

Subgroup analysis may also be performed for key demographic subgroups (e.g. age, gender, ethnicity) by adding interaction terms to the logistic regression or Cox regression model, where the sample size is deemed sufficiently large.

Where available, a meta-analysis, including data from existing SWATs will be undertaken to incorporate the results from this SWAT.

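### The recruitment SWAT names no blocking or stratifier for its site allocation and fixes a model with no site-level covariate; using site phase in both would be a cheap gain in precision if recruitment differs between pilot and main-phase sites

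*Protocol*

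**What the plan says.** **Allocation.** Protocol 4.5.1 makes the site the unit of randomisation: "randomisation will be carried out at the site level to reduce cross contamination. The allocation ratio will be 1 to 1". On how the sequence is made it adds only this: "Generation of the allocation sequence will be undertaken independently by a researcher not involved with the recruitment of participants". Blocking, stratification and minimisation are not mentioned. Section 4.5 points elsewhere for more: "The protocols for each are available on the MRC SWAT repository". For this SWAT that means SWAT 15, which was not available for this review.

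**Analysis.** Section 10.6.1 sets the primary analysis as "mixed effect logistic regression with a fixed effect for SWAT allocation and a random intercept for site". Site characteristics, with location and catchment size as the examples, are to be summarised but do not enter the model.

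**Kinds of site.** Section 4.1 says: "The pilot study will be set up in sites with existing surgical, rehabilitation and prosthetic experience of TKA". Other sites are given time for training and support. Section 8.0 offers TKA training to centres joining in the main phase where they need it. Section 10.2 plans 12 pilot sites. No total number of sites is given.

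**The other SWAT.** In 4.5.2, participants in the retention SWAT are "allocated 1:1 using block randomisation, stratified by" host-trial arm, with varying block sizes and the stated purpose of avoiding imbalance. Section 10.6.2 then includes the stratifier in the model.

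**The concern.** A cluster-randomised comparison has only as many randomised units as it has sites, so a single allocation can easily put more of one kind of site in one arm. Here the protocol itself creates a two-way split, pilot or main phase, that is known before each site is allocated. If the proportion of approached patients who are randomised differs between the two kinds, part of the between-site variance could be removed by design and by one model term. The protocol does this for the retention SWAT, which randomises individuals and so has many more units, but not for the recruitment SWAT.

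At stake are the width of the confidence interval for the animation effect, how far the one realised allocation might mislead, and the weight that the result can carry in the meta-analysis planned in 10.6.1.

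**Working it through.** **1. Figure to reproduce.** There is none. Section 4.5.1 says that no formal power calculation was done for this SWAT.

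**2. Number of sites (inferred).** Section 10.1 gives 386 participants over 36 months. Section 10.2 gives 77 in the 12-month pilot and one participant per two site-months, a rate of 0.5. The main phase therefore needs (386 − 77)/24 = 12.875 participants a month, and 12.875/0.5 = 25.75, or about 26 open sites. I take these as 12 pilot and 14 later sites. At a rate of 1.0 the figure would be about 13.

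**3. Chance imbalance.** I read the silence as unstratified 13 v 13 allocation. The number of pilot sites in one arm, X, is then hypergeometric (26 sites, 12 pilot, 13 drawn).
- Var(X) = 13 × (12/26) × (14/26) × (13/25) = 1.68. The difference between arms in the share of pilot sites is (2X − 12)/13, with SD 2 × √1.68/13 = 0.199.
- A difference of 30 percentage points or more needs X ≤ 4 or X ≥ 8. Its probability is 2 × 1,236,340/10,400,600 = 0.24.
- One SD of imbalance moves the estimate by 0.199 × 0.5 = 0.10 logits if the pilot-main gap is 0.5, and by 0.20 if it is 1.0.

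**4. Rough standard error.** Assumptions that are not in the protocol: 30 approached per site, 50% recruited, residual site SD 0.4 logits.
- Variance of a site logit: 0.4² + 1/(30 × 0.25) = 0.160 + 0.133 = 0.293.
- Variance of the arm difference with phase balanced: 2 × 0.293/13 = 0.0451, so SE 0.212.
- Unstratified, add 0.199² × gap² = 0.0398 × gap². The SE becomes √(0.0451 + 0.0099) = 0.235 at gap 0.5 and √(0.0451 + 0.0398) = 0.291 at gap 1.0.

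**5. Simulation of the stated model.** Logistic with a random site intercept, no true animation effect, 800 runs per cell, same assumptions. 'Fix' means allocation stratified by phase plus phase as a fixed effect.

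| Gap (logits) | Mean model SE, as written | Mean model SE, fix | SE ratio | Variance ratio | SD of estimates, as written | SD of estimates, fix |
|---|---|---|---|---|---|---|
| 0 | 0.205 | 0.202 | 1.01 | 1.03 | 0.210 | 0.225 |
| 0.5 | 0.226 | 0.202 | 1.12 | 1.25 | 0.236 | 0.219 |
| 1.0 | 0.287 | 0.204 | 1.41 | 1.98 | 0.302 | 0.215 |

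The mean estimate lies between −0.01 and 0.01 in every cell, so there is no bias over allocations. As written, the model SE follows the actual spread of the estimates closely. Each SD carries a simulation error of about 1/√1600 = 2.5%. Judged by the spread instead of the model SE, the gain at gap 0.5 is smaller (0.236/0.219 = 1.08), the gain at gap 1.0 is the same (0.302/0.215 = 1.40), and at gap 0 there is none.

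**6. Smaller case.** With 6 pilot and 6 main-phase sites (hypothetical), the model SE goes from 0.288 to 0.274, 0.317 to 0.279 and 0.403 to 0.276 for the same three gaps.

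**The case against.** The strongest objection is that the point rests on silence. Section 4.5.1 does not say that allocation is unrestricted, and restriction may be set out in SWAT 15 or another plan. This stands for the allocation: it is possible that sites will be stratified. Two things weaken it. The reference list dates the SWAT 15 entry to 2013, before this trial, so it is unlikely to define this trial's pilot and main-phase strata. And the model is not left open: 10.6.1 specifies it without a site-level term.

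The second objection is that no recruitment difference is documented. Sections 4.1 and 8.0 separate sites by TKA experience, and 4.2 requires every site to be able to perform both operations. Nothing states that the proportion recruited differs by phase. This stands in full. There are reasons to expect some difference, for example 10.5, where pilot interviews are to inform changes to recruitment materials, but its size is assumed. At zero gap the change buys nothing.

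Third, the SWAT is openly unpowered, and a wider standard error simply earns less weight in a meta-analysis. That limits the importance of the point without making the lost precision useful.

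A reader might infer more than the protocol supports:
- **That site differences bias the animation effect or are missing from its error.** They do neither. Sites are randomised, and the random intercept carries between-site variation, including any phase gap, into the standard error.
- **That imbalance would swamp any realistic animation effect.** The protocol gives no effect size to compare with.
- **That an uneven split of the 12 planned sites shows the problem.** Those are all pilot sites, so such a split is an imbalance in arm size, not in phase, and coin-toss allocation is nowhere stated.

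A separate matter is that z-based tests in the simulation rejected in 6.5% to 8.4% of null runs with 26 sites and in 9% to 11% with 12. These rates were much the same after the fix (6% to 8% and 9% to 11%), so the excess comes mainly from the small number of clusters, not from the missing stratifier.

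**Conclusion.** The point holds as a conditional, low-cost improvement to an embedded sub-study. As written, the protocol leaves the site allocation without a named stratifier and the primary model without a site-level covariate, although a natural stratifier is known for every site in advance.

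The consequence is possible chance imbalance and lost precision. At an assumed pilot-main gap of 0.5 logits (odds ratio 1.65) the model standard error is about 12% larger than it need be. At 1.0 (odds ratio 2.72) it is about 41% larger, equivalent to having roughly half as many sites. At zero gap the difference is negligible. These sizes rest on the inferred 26 sites, on the assumed numbers approached and recruited and residual site variation, and on reading the silence as unstratified 1:1 allocation. The host trial's primary outcome and analysis are untouched.

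**What to change.** - **Section 4.5.1:** state that sites are allocated in small random blocks, stratified by phase (pilot or main), as each site is ready to open. If SWAT 15 or another document already fixes a restricted scheme, say so here.
- **Section 10.6.1:** add phase as a fixed effect in the primary model.
- **If some sites are already allocated:** stratify the remaining sites and adjust for phase in all of them.

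The cost is about two sentences and roughly one site-level degree of freedom. No new data are needed, since the phase of each site is known.

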4.5.2 Retention SWAT: A cash vs voucher monetary incentive

Poor participant retention rates can have adverse consequences on the validity of randomised trials. There is a lack of evidence on efficient ways to retain participants in trials.

Monetary incentives consisting of either shopping/gift vouchers or cash are a common strategy used by trial teams to encourage participants to complete follow-up

questionnaires, attend follow-up assessment appointments or both. A previous review of strategies to improve retention in trials found monetary incentives may improve retention rates compared with no incentive; but the certainty of the evidence was low [1]. As a result, evaluation of monetary incentives as a retention method requires further evaluation.

We will evaluate the effect of an unconditional £25 shopping voucher incentive compared with an unconditional £25 cash incentive, provided before the 12 and 24 month follow up questionnaire. Participants will be asked to confirm their voucher preference at Baseline so that this can be provided should the participant be randomised to receive the voucher intervention.

As is usual with embedded trials, the sample size is constrained by the number of patients approached about the study hence a formal power calculation to determine sample size has not been conducted.

All participants recruited into the HAMLET trial, who remain as fully participating (i.e. have not fully withdrawn, withdrawn from postal follow up or have died) and who have yet to reach the 12-month time point will be eligible for the SWAT. There are no additional inclusion or exclusion criteria.

Generation of the allocation sequence will be undertaken independently by a researcher not involved with the follow up of participants. Participants will be allocated 1:1 using block randomisation, stratified by the host trial's treatment arm, using randomly varying block sizes to avoid imbalance between the SWAT intervention arms.

The primary outcome of this embedded trial will be retention rate, i.e. the proportion of participants who return their questionnaire in each group.

Secondary outcomes will be:

- 1) Cost-effectiveness (cost per participant retained)
- 3) Number of contact attempts with participants before completion of follow-up

assessment

4) Questionnaire completeness (e.g., primary outcome measure obtained)

The effects of the strategies in different patient populations will be explored, including sex, age and ethnic subgroups.

The acceptability of vouchers vs cash as an incentive will be explored with consenting participants as part of the embedded HAMLET Process Evaluation. Data will be shared with the IMPLEMENT SWATs team at the University of York for inclusion in a wider process evaluation of this intervention.

5.0 Study population

The target population for the HAMLET study will be patients who require a MLLA and are suitable for TKA and AKA but are unsuitable for BKA. To ensure the study results are representative of all those requiring a MLLA, all adult patients requiring a MLLA for any reason will be eligible.

